13.3.1 Investigator Responsibilities

Investigator responsibilities are set out in the ICH guideline for Good Clinical Practice (GCP) and in the US Code of Federal Regulations. Investigators must enter study data onto CRFs or other data collection system. The Investigator will permit study-related monitoring visits and audits by Celgene Corporation or its representatives, IRB/EC review, and regulatory inspection(s) (e.g., FDA, EMEA, TPP), providing direct access to the facilities where the study took place, to source documents, to CRFs, and to all other study documents.

The Investigator, or a designated member of the Investigator's staff, must be available at some time during monitoring visits to review data and resolve any queries and to allow direct access to the subject's records (e.g., medical records, office charts, hospital charts, and study related charts) for source data verification. The data collection must be completed prior to each visit and be made available to the Celgene Pharmaceuticals, Inc. representative so that the accuracy and completeness may be checked.

14.0 STATISTICAL CONSIDERATIONS

14.1 Study Design/Primary Endpoint

The study is a randomized phase III design, and the primary endpoint in both treatment arms is median PFS. PFS will be defined as the time from randomization day until objective progression or death from any cause. The PFS distributions of the two treatment arms will be estimated by Kaplan-Meier survival analysis and the PFS distributions will be compared by an unstratified log-rank test. Ninety-five percent confidence intervals for the Kaplan-Meier PFS estimates will be calculated using

Greenwood's formulae. The primary comparison will be made using the intent-to-treat (ITT) patient population. Patients will be analyzed based on their randomization assignments, regardless of therapy initiation or compliance. A secondary analysis will be performed comparing "evaluable" patients as patients who met eligibility requirements, have initiated therapy, and were not removed from the study for non-compliance or patient withdrawal.

The median PFS for MM patients receiving Revlimid /dexamethasone chemotherapy (Rd) (Arm A) is expected to be approximately 25.5 months, as reported in the MM-010 study of continuous Rd vs Rd for 18 months (Facon T, Dimopoulos M, Dispenzieri A, et al: Initial phase 3 results of the FIRST trial in newly diagnosed multiple myeloma patients ineligible for stem cell transplant. 2013 ASH Annual Meeting. Abstract 2. Presented December 8, 2013.). Therefore, the target median PFS for patients receiving Revlimid/dexamethasone/Clarithromycin (BiRd) (Arm B) is hypothesized to be 44.6 months (target hazard ratio = 1.75).

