3.2 Prognosis

The overall median survival for patients with MM is 36 months, with International Staging System stage I, II, and III patients surviving a median of >60, 41, and 23 months respectively.⁴ Several prognostic factors have been identified. An elevated serum level of beta-2 micro-globulin (β2M), a component of the class I HLA molecule, is a powerful prognostic indicator of shortened survival.⁵ Since β2M is excreted by the kidney, renal insufficiency will increase serum levels of β2M. The plasma cell labeling index (PCLI) identifies the percentage of proliferating plasma cells in S phase of the cell cycle and is a powerful independent predictor of progression and survival.⁶ Chromosomal abnormalities, such as translocations t(4;14), del 17p, and t(14;16) confer poor prognosis.^{7,8} Investigators have found that achieving a complete remission early on in the disease may be important in predicting long-term survival.^{9,10} Indeed, Kyle *et. al* suggested that an objective response to standard therapy is by far the most important feature of long-term survivors.¹¹ Major controlled trials have confirmed this seminal observation even in the context of high-dose chemotherapy.¹² Based on those observations, the goal of achieving an early complete remission should allow patients to sustain long-term survival and perhaps lead to a cure.

Myeloma is still an incurable disease and obtaining an initial long disease-free interval prior to relapse is important to prolong patient survival and improve quality of life. At the present time, there is still a need for new and effective induction therapies for the newly diagnosed multiple myeloma patients to achieve this goal.

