13.0 DATA MANAGEMENT

13.1 Analyses and Reporting

This study will be conducted at The New York Presbyterian Hospital at the Weill Cornell Medical College. Clinical data will be collected under the supervision of one of the study investigators. Clinical data will be organized and recorded with the help of data managers located at the Cornell campus. Study design and data analysis will be implemented in collaboration with our biostatistician at Weill Cornell Medical College and data will be collected and tabulated on a monthly basis.

13.2 Data Safety Monitoring Board.

The Data Safety Monitoring Board (DSMB) at Weill-Cornell Medical Center will be composed of medical and statistical independent reviewers and will meet to review the efficacy and safety data and determine a risk/benefit analysis in this subject population. The purpose of the DSMB is to advise on serious safety considerations, lack of efficacy and any other considerations within the charge to the Committee. The DSMB may request additional meetings or safety reports as deemed necessary upon discussion with Celgene and its representatives. The PI, [name], will be the safety contact for all DSMB related analysis outcomes.

[name] office is located at: NYPH-WCMC
[name]
[name]

The phone number to [name] office is: [contact]

The DSMB may stop the study following review of results from each interim analysis. The first interim analysis will take place 3 months after the study begins subject accrual or after 10 patients have been enrolled, whichever occurs first, and will examine only safety information. A subsequent interim analysis will take place 6 months after the study begins subject accrual, and every six months thereafter, and will examine both safety and efficacy. The DSMB will also review the study after 66 PFS events have occurred across both arms for futility, (as outlined in the Statistical Considerations Section 14) including toxicity data, protocol adherence, and protocol deviations and enforce stopping rules if necessary. Efficacy and safety data summaries will be provided to the DSMB after each interim analysis.

“13.3 Study Monitoring and Auditing

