14.2 Sample Size/Accrual Rate

To achieve 90% power to detect a 75% increase in median PFS (44.6 vs. 25.5 months), at the two-sided 0.05 significance level, will require 306 patients total, accrued over approximately 3.0 years (assuming an accrual rate of approximately 9 patients/month), with an additional 12 months of follow-up subsequent to termination of accrual.

When the sample size in each group is 153 patients, with a total number of PFS events required of 133, an exponential maximum likelihood test of equality of survival curves with a 0.05 two-sided significance level will have 90% power to detect the difference between an Arm A (Rd) median PFS of 25.5 months and an Arm B (BiRd) median PFS of 44.6 months (a constant hazard ratio of 1.75); this assumes an accrual period of 3.0 years, a maximum follow-up time of 4.0 years, and no dropouts. The exponential assumption is for planning purposes only, actual analysis will employ nonparametric methods for estimation and testing of survival distributions. Assuming a 10% dropout rate, approximately 337 patients will be accrued to the study.

A futility analysis will be conducted after 50% of the total PFS events required for final analysis has occurred (i.e., 66 of the 133 required PFS events). No accrual suspension is required to conduct the futility analysis. If at this point (i.e., after accumulation of 66 PFS events) the hazard ratio of the control arm over the experimental arm is 1.0 or less, the study will be stopped for futility.

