14.3 Stratification Factors

Patients will be stratified based on enrolling institution.

Blocked randomization will be performed at all participating sites. A series of randomized blocks will be generated for each participating site with a 1:1 allocation ratio. This will provide assurance that there will be an equal patient allocation to both treatment arms at any given participating site.

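### The primary PFS test ignores the randomisation factor (institution) and ISS stage: type I error is safe, but a few points of power may be given up

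*Combined protocol and SAP*

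**What the plan says.** - **Randomisation.** Section 14.3 (Stratification Factors): "Patients will be stratified based on enrolling institution", and "A series of randomized blocks will be generated for each participating site with a 1:1 allocation ratio". Block size and number of sites are not given.
- **Primary test.** Section 14.1: "the PFS distributions will be compared by an unstratified log-rank test". No reason is offered for leaving the randomisation factor out.
- **Sensitivity analyses.** Section 14.3 (Analysis of Progression-Free Survival) varies event and censoring rules (Tables A to C) and adds a check for evaluation-time bias. None of these analyses is stratified or covariate-adjusted.
- **Sites.** Section 13.1: "This study will be conducted at The New York Presbyterian Hospital at the Weill Cornell Medical College". The stratification section speaks of participating sites in the plural, and sections 9.3.2, 10.11.2 and 15.6 also presuppose more than one centre.
- **ISS.** Section 3.2 reports "International Staging System stage I, II, and III patients surviving a median of >60, 41, and 23 months respectively". Appendix II defines the stages. Both components, beta-2-microglobulin and albumin, are in the screening assessments (1.3, 6.1). Neither randomisation nor analysis uses ISS.

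**The concern.** Blocking within institution forces the arms to be nearly balanced in every site. If sites differ in prognosis, that balance removes a source of chance variation from the treatment contrast. An unstratified log-rank variance still counts that variation, so the statistic varies less than its nominal standard normal and the test rejects too seldom. Pooling patients of different prognosis also dilutes a hazard ratio that holds within site or stage. Both effects reduce power.

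ISS is a separate matter. It is not a randomisation factor, so leaving it out creates no mismatch between design and analysis. But a prognostic baseline measure that is already collected can recover power and guard against chance imbalance. The design has no power to spare: the plan's own events give just about 90%.

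**Working it through.** **1. The plan's figure.** Inputs from 14.2: hazard ratio 1.75, two-sided alpha 0.05, 90% power, 1:1 allocation, 133 events, 306 patients.

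Events (Schoenfeld) = 4(1.960 + 1.282)² / (ln 1.75)² = 42.03 / 0.3132 = 134.2, so 135 against 133 stated.

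Power at 133 events = Φ(½ × √133 × 0.5596 − 1.960) = Φ(1.267) = 89.7%.

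The figure reproduces. The calculation contains no strata and no covariate.

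**2. Site stratification.** The documents give neither the site effect nor the number of sites, so both are assumptions. Simulation: 306 patients, analysis at 133 events, blocks of 4 within site, exponential PFS. Runs per row: 10,000 (Monte Carlo error about 0.2 points for alpha and 0.3 for power), or 3,000 where marked * (about 0.4 and 0.6).

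| Sites | Site log-hazard SD | Alpha %, unstratified → stratified | Power %, unstratified → stratified | Change in power (points) |
|---|---|---|---|---|
| 5 | 0.2 | 4.9 → 5.0 | 88.4 → 88.6 | +0.2 |
| 15 | 0.2 | 4.7 → 4.8 | 89.1 → 88.3 | −0.8 |
| 30 | 0.2 | 4.7 → 5.0 | 88.4 → 86.0 | −2.4 |
| 5 | 0.6 | 4.0 → 5.2 | 84.9 → 88.3 | +3.4 |
| 15 | 0.6 | 3.4 → 5.0 | 84.7 → 87.5 | +2.8 |
| 30* | 0.6 | 3.6 → 4.8 | 84.2 → 85.8 | +1.5 |
| 30* | 0 | 5.4 → 5.3 | 89.5 → 86.7 | −2.8 |

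At SD 0.4 (3,000 runs) the change was +2.0 points with 5 sites, +1.0 with 15 and −1.5 with 30. With one site the two tests are the same.

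Check on the mechanism: with 15 sites and SD 0.6, the null SD of the unstratified z was 0.932. This implies alpha = 2[1 − Φ(1.960/0.932)] = 2[1 − Φ(2.103)] = 3.5%, against 3.4% simulated. The stratified z had SD 1.003.

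Further runs (3,000 per setting) also included an ISS effect:
- At SD 0 to 0.3, unstratified alpha was about 5%.
- At SD 0.5, it was 3.9 to 4.5%. With 5 to 10 sites, stratifying by site gained about 1.5 to 2 points (for example 83.4–83.6% to 85.0–85.3%).
- With 20 sites and no site effect, unpooled strata lost about 2.7 points. Pooling sites with fewer than 20 patients cut the loss to about 1 point.

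**3. ISS stratification.** The section 3.2 medians, with stage I taken as 60 months, give log hazards relative to stage II of −ln(60/41) = −0.38 and ln(41/23) = +0.58. Stage mix 25/40/35% is assumed.
- Full gradient: power 86.9% → 88.9% (+2.0); alpha 4.9% → 5.0%.
- Half gradient: power 88.7% → 88.8% (+0.1).
- In the further runs (full gradient), ISS strata gained 1.4 to 2.6 points in every setting.

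**4. Both together.** A Cox model stratified by site with ISS as covariate gained about 2 to 4 points over the unstratified test with 5 to 10 sites. That rests on 800 runs (error about 1.3 points per power estimate), so it is only indicative.

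Crossing ISS with site thins the strata: 133 / (3 × 5) = 8.9 events per cell with five pooled sites, and 133 / (3 × 10) = 4.4 with ten.

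**The case against.** The case for leaving the plan alone has five parts.

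1. The unstratified test is pre-specified, matches the planning calculation and does not inflate type I error. This stands: the point concerns efficiency and coherence, not validity.
2. The stronger reading, that the p-value is conservative and power is lost, is tempting because the blocking and the test do not match. The documents do not support it as a fact. It needs sites that differ in prognosis, and no section says how much they do. SD 0.5 means that sites one SD above and one below average differ by exp(1.0) = 2.7-fold in hazard, about the ISS I-to-III contrast (60/23 = 2.6). Under common eligibility criteria that is a large difference.
3. Section 13.1 names one institution. With one site the point about institution disappears. Other sections point to several, but the count is missing.
4. Site stratification can cost power with many small sites. This stands, and is why a pooling rule belongs in the fix.
5. The medians in 3.2 are for overall survival, and the stage mix is assumed. This also stands, and explains why the ISS gain is given as a range starting near zero.

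A reader might also credit the site-stratified log-rank test alone with a gain of 2 to 4 points. That figure belongs to a model that includes ISS.

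None of this supplies a reason for omitting the randomisation factor from every planned PFS analysis.

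**Conclusion.** The point holds as an inexpensive improvement with a conditional benefit. The primary test, and every other planned PFS analysis, ignores the randomisation factor and a derivable prognostic stage.

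- **Validity:** type I error is not inflated.
- **Institution:** at an assumed site SD of about 0.5 to 0.6, alpha falls to about 3.4 to 4.5% and about 1 to 3 points of power are given up. At SD 0.3 or below there is little or no loss. With one site there is none.
- **ISS:** adjustment gains about 0 to 2.6 points, assuming the overall-survival gradient applies to PFS at full or half strength.

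These sizes rest on assumed site effects, site numbers and stage mix, and on a hazard ratio of 1.75. The exact recommended test, a log-rank stratified by ISS and pooled site together, has no power figure of its own here.

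**What to change.** 1. In 14.1, make the primary PFS test a log-rank stratified by ISS stage and by enrolling institution. Equivalently, use the treatment test from a Cox model stratified by pooled site with ISS as a covariate, which avoids thin cross-classified cells. Either way, ISS must enter the test and not only the hazard ratio.
2. State the number of sites. Fix a pooling rule before unblinded data are seen; for example, sites with fewer than 20 patients form one stratum.
3. Take the hazard ratio from the matching Cox model. Section 14.2 bases the futility rule on a hazard ratio but names no model, so say there which one applies.
4. Keep the unstratified log-rank as a sensitivity analysis.
5. Record ISS stage as a derived baseline variable with a rule for missing components. Correct the stage II row of the ISS table in Appendix II, which as it reads defines stage II by reference to itself.

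**Cost:** wording and one derived variable; no new data. If sites do not differ, site strata cost about 0 to 1 point of power with pooling, and up to about 3 points with 20 to 30 small sites left unpooled. The choice should be settled early: the trial is open-label, and strata chosen after results by arm are known would be open to criticism.

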4.0 INVESTIGATIONAL PLAN

4.1 Study Design

This phase III study, open-label, randomized study investigating lenalidomide and dexamethasone with and without bixin in subjects with newly diagnosed, previously untreated multiple myeloma. Eligible subjects will be randomized in a 1:1 ratio to receive a regimen consisting of either bixin, lenalidomide, and low dose dexamethasone (BiRd arm), or lenalidomide and low dose dexamethasone (Rd arm). Up to 306 patients will be enrolled.

BiRd Arm

Subjects on the BiRd arm will receive bixin, revlimid, and dexamethasone in 28-day cycles. Dosing is as follows:

- Clarithromycin 500mg PO twice daily on days 1-28 for a 28-day cycle. If a dose of clarithromycin is missed, it should be taken as soon as possible on the same day. If it is missed for the entire day, it should not be made up. Vomited doses will not be made up.
- Lenalidomide 25mg PO daily on days 1-21 of a 28-day cycle for patients with a calculated creatinine clearance of ≥ 60 cc/min. Patients with a calculated creatinine clearance of < 60 cc/min will receive 15 mgs PO daily on days 1-21 of a 28 cycle. If a dose of lenalidomide is missed, it should be taken as soon as possible on the same day. If it is missed for the entire day, it should not be made up. Vomited doses will not be made up.
- Dexamethasone 40mg PO will be given on days 1, 8, 15, 22 of a 28-day cycle. Missed or vomited doses will not be made up. If subject cannot tolerate oral dexamethasone, it will be given intravenously.

Rd Arm

Subjects on the Rd arm will receive revlimid, and dexamethasone in 28-day cycles. Dosing is as follows:

- Lenalidomide 25mg PO daily on days 1-21 of a 28-day cycle for patients with a calculated creatinine clearance of ≥ 60 cc/min. Patients with a calculated clearance of < 60 cc/min will receive 15 mgs PO daily on days 1-21 of a 28 cycle. If a dose of lenalidomide is missed, it should be taken as soon as possible on the same day. If it

is missed for the entire day, it should not be made up. Vomited doses will not be made up.

- Dexamethasone 40mg PO will be given on days 1, 8, 15, 22 of a 28-day cycle. Missed or vomited doses will not be made up. If subject cannot tolerate oral dexamethasone, it will be given intravenously.

Correlative studies: Relative dose intensity: Projected total dose per cycle of each component of assigned drug will be divided by the actual dose received and a ratio will be assessed for each cycle delivered.

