10.4 Post Study Follow-up

All attempts will be made to follow patients until progression or death. Subjects who have been discontinued from study will still be followed in a clinic setting to the fullest extent possible on a monthly to bi-monthly basis. Those who choose not to resume regular clinic follow-up will be contacted every 6 months by telephone or electronically

to collect post study information. The post-study collection information will consist of a telephone interview between the clinical investigator and the discontinued patient. The information requested will be current disease status including information about the development of secondary primary malignancies, current treatment use, and physical status of the patient.

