10.11 Criteria for removal from study

Rules for termination of the study for the individual subject are listed below:

- Subjects may withdraw consent and stop participation at any time.
- Any Grade 4 skin toxicity (i.e. Stevens Johnson syndrome) or Grade 4 hypersensitivity (i.e. anaphylaxis).
- Progression of multiple myeloma, as defined by the International Myeloma Working Group Criteria (Appendix 1 of the protocol).
- Development of any co-morbid condition or excessive toxicity that would make further participation in the protocol unsafe.
- The development of any comorbid condition of excessive toxicity that would make further participation in the protocol unsafe.
- Non-compliance or refusal of the patient to continue treatment and/or evaluation.
- Major violation of the study protocol.
- Any adverse event(s) that, in the judgment of an Investigator, may cause severe or permanent harm if the study medications are continued.
- At the discretion of the principal investigator and/or Celgene Pharmaceuticals, Inc. for any reason.
- Loss to follow up.
- Death of patient

Any possible premature discontinuation would be documented adequately with reasons being stated, and information would have to be issued according to local requirements (e.g., IRB/EC, regulatory authorities, etc.).

10.11.2 The responsible Clinical Investigator as well as Celgene Pharmaceuticals, Inc. have the right to discontinue this study at any time for reasonable medical or administrative reasons in any single center. Possible reasons for termination of the study could be but are not limited to:

- Unsatisfactory enrollment with respect to quantity or quality.
- Inaccurate or incomplete data collection.
- Falsification of records.
- Failure to adhere to the study protocol.

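### The secondary evaluable PFS comparison deletes patients for a later event (removal for non-compliance or withdrawal), which can bias it in either direction; the primary ITT test is not affected

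*Combined protocol and SAP*

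**What the plan says.** Section 14.1 sets the primary analysis clearly: "The primary comparison will be made using the intent-to-treat (ITT) patient population", and "Patients will be analyzed based on their randomization assignments, regardless of therapy initiation or compliance". It names median PFS as the endpoint and specifies Kaplan-Meier estimates and a log-rank test.

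The same section then adds a further comparison: "A secondary analysis will be performed comparing 'evaluable' patients as patients who met eligibility requirements", who also "have initiated therapy, and were not removed from the study for non-compliance or patient withdrawal". It does not say whether a hazard ratio will be reported for this set.

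The exclusion is fed by section 10.11, which allows withdrawal of consent at any time and lists as another ground "Non-compliance or refusal of the patient to continue treatment and/or evaluation". Neither is tied to a time point. Section 10.4 states that "All attempts will be made to follow patients until progression or death", so outcome data on removed patients may exist.

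No section gives expected removal by arm, a method for the selection, or a caution on reading the evaluable result.

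**The concern.** Of the three conditions, eligibility can be judged from baseline data. Starting therapy is settled early, although it too comes after randomisation. Not being removed is settled only at the end of follow-up. A patient with an early event has little time in which to be removed and is kept. A patient who stays progression-free has a long time in which to be removed and, if removed, is deleted from day 1. Only patients without an event are dropped, so PFS in the retained set looks worse than it is. The arm that loses more patients is penalised more.

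Unequal removal is plausible. The trial is open-label and BiRd adds a twice-daily drug. What is at stake is the only comparison in section 14 made in a population other than ITT. Its difference from the ITT result could come from the deletions and not from compliance.

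**Working it through.** **1. The plan's own figures (section 14.2).** Medians of 25.5 and 44.6 months give hazards λ = ln 2/25.5 = 0.0272 (Rd) and ln 2/44.6 = 0.0155 (BiRd) per month, ratio 1.75.
- Schoenfeld events: 4(1.960 + 1.282)²/(ln 1.75)² = 134.2, against 133 stated.
- Power with 133 events: Φ(√133 × ln 1.75/2 − 1.960) = 0.897, against 0.90.
- Expected events by month 48 with uniform accrual over 36 months: 153 × (0.540 + 0.364) = 138.

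The design reproduces, and the evaluable definition does not enter it.

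**2. What deletion does to the hazard.** Let q(t) be the probability that a patient still at risk at time t reaches an event or data cut-off without being removed. If removal is unrelated to prognosis, the hazard in the retained set is λ/q(t), always at least λ. The hazard ratio (Rd over BiRd) becomes 1.75 × q_BiRd(t)/q_Rd(t). At t = 0, q is one minus the proportion excluded. As the remaining follow-up shrinks, q tends to 1 and the ratio returns to 1.75.

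**3. Proportion excluded.** With removal hazard w, it is w/(w+λ) × {1 − [e^(−12(w+λ)) − e^(−48(w+λ))]/[36(w+λ)]}. The values of w are assumptions. With w = 0.005 (Rd) and 0.010 (BiRd) per month this gives 0.093 and 0.203. The ratio at time zero is then 1.75 × 0.797/0.907 = 1.54, so the average must lie between 1.54 and 1.75.

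**4. Simulation.** 153 per arm, exponential PFS, administrative censoring uniform on 12 to 48 months, removal unrelated to prognosis, two-sided log-rank test at 0.05. A patient is deleted if removal precedes event and cut-off.

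| Analysis | Excluded Rd/BiRd | HR | Power |
|---|---|---|---|
| All kept, full follow-up | none | 1.75 | 90% |
| Evaluable as written | 7%/14% | 1.67 | 82% |
| Evaluable as written | 9%/20% | 1.61 | 75% |
| Same removals as 9%/20%, censored at removal | none | 1.75 | 87% |
| Evaluable, same removal rate in both arms (0.5%/month) | 9%/11% | 1.74 | 87% |
| Evaluable, more removed from Rd | 15%/5% | 1.89 | 95% |

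The 7%/14% row averages about 10%, the overall dropout figure in section 14.2. The fourth row shows that deletion, not removal, moves the estimate.

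**5. No true effect (25.5 months in both arms).** Evaluable HR is about 0.94 with 9%/17% excluded, 0.93 with 5%/15% (two-sided type I error 0.08), 0.89 with 5%/20% (0.12), 1.08 with 15%/5% (0.07), and 1.00 with 10%/10% (0.05). If about 9–10% are removed per arm but removal is four times as likely in the poor-prognosis half of one arm only, HR is 1.04 when that arm is BiRd and 0.96 when it is Rd.

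**6. Medians.** With 0.5% per month removed in both arms, the evaluable Kaplan-Meier medians fall from 25.5 to 23.8 months and from 44.6 to about 42. Censoring at removal leaves both unchanged.

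**The case against.** The strongest case is that little harm follows. Bias in the hazard ratio needs removal that differs by arm or is linked differently to prognosis by arm, and no section gives such rates. With equal removal unrelated to prognosis the ratio is almost unchanged. A reader might infer that the evaluable analysis is bound to give a biased hazard ratio. The documents do not support that: size and direction are unknown, and section 14.1 does not commit to reporting a hazard ratio for this set.

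The documents also limit how far the arms may diverge. Toxicity is not one of the excluding reasons. Section 4.1 continues the remaining agents when toxicity precludes one, so a BiRd patient who stops clarithromycin for toxicity need not be removed. The maintenance regimen in section 9.1 names only lenalidomide and dexamethasone, although section 4.1 continues randomised treatment to progression. The 9%/20% case exceeds the plan's overall 10% dropout.

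A reader might also infer that the evaluable result will be taken as confirming the ITT result, or could reverse a true benefit. Section 14.1 calls it only a secondary analysis, and robustness of PFS is assigned to the sensitivity analyses in section 14.3. In the 9%/20% case the ratio still favours BiRd at about 1.6, and in a 2,500-trial run no trial was significant in the wrong direction.

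All of this stands, and it lowers the weight of the point. It does not remove the selection, which is in the definition itself, nor the downward shift in the medians.

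**Conclusion.** The point holds as a minor one. The evaluable set selects on a post-randomisation event and can bias the secondary PFS comparison in either direction; no other section corrects this. At exclusions consistent with the plan's 10% dropout (7%/14%, Rd/BiRd), the hazard ratio moves from 1.75 to 1.67 and power from 90% to 82%. At 9%/20% they are 1.61 and 75%. With no true effect and 9%/17% excluded the ratio is about 0.94. All of this rests on assumed arm-specific removal rates, exponential PFS, and removal unrelated to prognosis except where stated. It also assumes one recorded reason for removal, so that a patient who progresses first is kept.

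Nothing here weakens the primary ITT comparison: its test, its 133 events and its power do not depend on the evaluable definition. The 90% reference assumes that removed patients are followed to an event. Table A in section 14.3 instead censors at discontinuation for other reasons, which is a separate matter.

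**What to change.** In section 14.1, end the evaluable definition before the removal condition. Keep removed patients in their assigned arm, with their time counted at least up to removal and then handled by the same censoring rules as Tables A to C in section 14.3. Label the analysis supportive. Report the number removed by arm and by reason, so that a reader can judge whether the arms differ.

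If an on-compliance estimate is wanted, censor at removal instead of deleting the patient, optionally with inverse-probability-of-censoring weights. State that having started therapy is also a post-randomisation condition, and report by arm how many patients it excludes.

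The cost is one revised sentence and one short table, with no new data collection and no change to the primary analysis. The downside is that the set lies closer to ITT and says less about compliance; the optional censored analysis answers that question.
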